### **10.2 Primary study parameter(s)**

The primary effect parameter will be expressed by a common odds ratio, estimated with ordinal logistic regression, evaluating a shift on the mRS score at 90 days after randomization. The common odds ratio will be estimated with proportional odds regression adjusted for age, baseline NIHSS score, pre-stroke mRS score, collateral score on baseline CTA and onset to reperfusion time. Both unadjusted and adjusted estimates will be reported with 95% confidence intervals.

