**Main study parameters/endpoints:** the primary endpoint is the modified Rankin Scale (mRS) score at 3 months after stroke onset. Ordinal logistic regression analyses will be done with adjustment for prognostic variables: age, sex, baseline NIHSS, prestroke mRS score, collateral score on baseline CTA and onset to reperfusion time.

**Nature and extent of the burden and risks associated with participation, benefit and group relatedness:** All patients are being treated with EVT according to the local guidelines. The patients allocated to the intervention group will undergo CAS during EVT, which carries a risk of cerebral hyperperfusion syndrome and subsequent intracerebral hemorrhage. The potential benefits of immediate CAS during thrombectomy include: an improvement of cerebral blood flow during and after EVT. A second benefit is a lower risk of recurrent stroke in the first 14 days compared to the deferred treatment strategy. A third benefit of immediate CAS is that the patient does not need a second invasive treatment (carotid revascularization surgery (CEA or CAS) during the rehabilitation period which again carries some risk of complications. At last, the immediate CAS approach is likely to reduce health care costs.

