For the sample size calculation, we used data from the Dutch MR CLEAN registry, a nationwide cohort of EVT treated patients between 2014-2018. Based on the mRS distributions in the immediate CAS group (mRS 0: 17.9%, mRS 1: 22.3%, mRS 2: 16.7%, mRS 3: 14.4%, mRS 4: 12.3%, mRS 5: 5.0%, mRS 6: 11.4%) and in the deferred treatment group (mRS 0: 6.9%, mRS 1: 20.2%, mRS 2: 17.9%, mRS 3: 16.4%, mRS 4: 17.2%, mRS 5: 8.0%, mRS 6: 13.4%), we calculated the assumed effect size to be a common odds ratio (cOR) of 1.15 for a shift in favorable direction on the full mRS. The non-inferiority margin was set to a cOR of 0.8, corresponding to an absolute difference of approximately 5% in favorable outcome (mRS 0-2). This is a generally accepted margin in the stroke research community and has been recently used in comparable EVT trials. We used Monte Carlo simulations with 5000 runs to calculate the required sample size based on the assumptions above showing that a sample size of 610 patients, would provide 80% power (at a two-sided alpha level of 0.05) to determine that the lower bound of the cOR 95% confidence interval (CI) does not cross the non-inferiority margin of 0.8. Covariate adjustment for major prognostic variables that included age, pre-stroke mRS score, stroke severity, collateral score and time from symptom onset to randomization results in a reduction of at least 15% in the required sample size (n=520). Assuming a crossover rate of 3% in each arm (6% for both groups), necessitates an increase in sample size by factor  $1/(1 - \% \text{ crossover})^2 = 1/(1 - 0.06)^2 = 1.13$ . So taking crossovers into account, the sample size increases to 588 (520\*1.13). Based on the experience of the MR CLEAN NO-IV trial and MR CLEAN-MED trial, the number of patients lost to follow up is expected to be low

(0 in both recently completed trials). Assuming a combined percentage of 2% due to loss to follow up and to erroneous inclusions (for example inclusion of patients who appear to have carotid dissection or carotid pseudo-occlusion) the sample size will need to be increased to a total sample size of 600 patients (n= 300 per group).

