## 5. TREATMENT OF SUBJECTS

### 5.1 Investigational product/treatment

In patients allocated to the intervention group, the carotid artery stenosis will be stented during the EVT. The CAS may be done just before the intracranial thrombus removal or directly after (at the discretion of the interventionist). In case of unsuccessful intracranial reperfusion (TICI score < 2b), it is still recommended to perform CAS. In addition, if the first DSA run demonstrates intracranial recanalization but confirms a high-grade carotid artery stenosis, it is still recommended to perform CAS. Crossover to deferred treatment is strongly discouraged and will be considered a protocol violation unless a valid reason has been reported by the local PIs.

The patients allocated to the control group are being treated with EVT, without stenting of the carotid artery stenosis. Percutaneous transluminal angioplasty (PTA) of the carotid artery stenosis is allowed to gain access in order to remove the intracranial occlusion. Crossover to stenting during EVT is strongly discouraged. Crossovers without a valid reason according to the executive committee will be considered a protocol violation. If the patient recovers to a non-disabling stroke after EVT, CEA or CAS is offered according to the guidelines (usually CEA or CAS within 2 weeks after stroke onset). In case of a persistent disabling stroke, patients receive best medical treatment, without intervention of carotid artery stenosis.

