#### **8.2 Randomization, blinding and treatment allocation**

The randomization will be performed by a computer and web-based procedure, using permuted blocks. Back-up by telephone will be provided. Randomization is allowed when the CTA at baseline demonstrates an ipsilateral high-grade stenosis (>50%) or occlusion of the proximal ICA of presumed atherosclerotic origin. Although DSA is more reliable to distinguish carotid pseudo-occlusions from cervical atherosclerotic lesions in the ICA, randomization during the EVT can be very challenging and might lead to lower inclusion rates. And CTA has been shown to have acceptable diagnostic accuracy for true cervical ICA lesions. Only in case of significant doubt by the interventionist if there is a true cervical atherosclerotic lesion in the carotid artery, randomization is also allowed after the first angiographic run of the carotid artery that confirms the cervical atherosclerotic lesion. Randomization will be stratified for center. Both the patient and treating physicians are aware of the treatment assignment. The 90 days follow up will be performed by certified research personnel blinded for the treatment allocation. The assessment of secondary endpoints will not be blinded as for several secondary endpoints it will be obvious whether the patient was treated with CAS or not. Information on treatment allocation will be kept separate from the main study database. An independent trial statistician will combine the data on treatment allocation with the clinical data in order to report to the data safety monitoring board (DSMB). The trial steering committee will be kept unaware of the exact results of the interim analyses on efficacy and safety. Only the recommendation to continue, modify or stop the trial will be communicated.

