### 11.2 Recruitment and consent

This trial will include patients using a deferred written informed consent procedure. This means that, after the treatment, written informed consent is obtained by asking the patient, or a legal representative of the patient. The justification for the deferred consent is as follows. Firstly, during acute ischemic stroke, the adagium “time is brain” holds. Reperfusion therapy should be initiated as soon as possible. For every hour delay, the chance of recovery to activities of daily living (ADL) independency decreases with 6%. It has been observed in previous acute stroke trials, that obtaining informed consent before start of the treatment, led to an (unacceptable) delay in treatment onset. Secondly, during the acute phase of acute ischemic stroke a patient is often unable to make a well thought out decision on whether to participate in a study, due to neurological deficits like language disturbances, unable to communicate or anosognosia (unaware of his or her medical condition). Obtaining consent from the patient’s proxy will also unacceptably delay the EVT itself. In summary due to the emergency situation as well as the lack of decision-making capacity, the trial cannot be performed without a deferred consent approach. This approach has been successfully used in recent acute stroke trials in the Netherlands.

After treatment, informed consent will be obtained by asking the patient or a legal representative of the patient, preferably within 24 hours after EVT. The patient and/or representative will be provided with a verbal and written explanation of the study by the local investigator. They will be asked for consent to use their data, biomaterials for the purpose of the study and to perform follow up investigations. Participation in the study is voluntary and at any given time, informed consent can be withdrawn. If the patient has died before informed consent has been obtained, the patient’s proxy’s will be informed about the study, the treatment the patient has received and the use of the data that has been collected. Because mortality is an important safety endpoint, data of these patients will be (anonymously) stored, in order to provide these data to the DSMB.

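### The primary model adjusts for onset-to-reperfusion time, which is normally fixed after randomisation and which stenting can change, so the non-inferiority estimate can be biased; the sample size section assumes a different, pre-randomisation time.

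*Protocol*

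**What the plan says.** Section 10.2 estimates the common odds ratio by proportional-odds regression "adjusted for age, baseline NIHSS score, pre-stroke mRS score, collateral score on baseline CTA and onset to reperfusion time". The Summary lists "age, sex, baseline NIHSS, prestroke mRS score, collateral score on baseline CTA and onset to reperfusion time", the same set plus sex. Section 4.5 uses another time variable when it reduces the sample size: "time from symptom onset to randomization results in a reduction of at least 15% in the required sample size".

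Three other passages decide whether the difference matters.

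- Section 8.2 places allocation early: "Randomization is allowed when the CTA at baseline demonstrates an ipsilateral high-grade stenosis (>50%) or occlusion of the proximal ICA". In case of significant doubt, randomisation may wait until after the first angiographic run.
- Section 5.1 leaves the order of the procedure open: "The CAS may be done just before the intracranial thrombus removal or directly after", at the interventionist's discretion.
- Section 11.2 links time to outcome: "For every hour delay, the chance of recovery to activities of daily living (ADL) independency decreases with 6" (a percentage).

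Section 10 requires both the per-protocol and the intention-to-treat analysis to show non-inferiority. Section 10.2 reports unadjusted and adjusted estimates and does not say which is compared with the margin of 0.8. Section 10.3 gives the secondary endpoints the same adjustments but cites 10.1, which contains none; the list is in 10.2.

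**The concern.** A covariate in the primary model of a randomised trial should be fixed before allocation. Onset-to-reperfusion time normally is not. It includes the interval from randomisation to reperfusion, in which the stent may be placed. By the protocol's own account this time affects recovery, so it can lie on the path from stenting to the mRS. Adjusting for it then compares the arms as if reperfusion had occurred at the same time in both, whereas the trial is meant to compare the strategies with all their consequences.

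The decision is a non-inferiority claim at a margin of 0.8. If stenting first delays reperfusion and thereby does harm, the model credits that harm to the covariate, and the treatment estimate moves towards non-inferiority. The same covariate would enter both the intention-to-treat and the per-protocol analysis, so requiring both to succeed does not remove the problem.

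**Working it through.** **1. The covariate lists side by side**

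| Place | Time covariate | Fixed before allocation? | Sex |
|---|---|---|---|
| Summary | onset to reperfusion | normally no | yes |
| 4.5 | onset to randomisation | yes | not named |
| 10.2 | onset to reperfusion | normally no | no |

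The step in 4.5 that depends on the list reproduces: 610 × 0.85 = 518.5, rounded to 520; 520 × 1.13 = 588; 588 / 0.98 = 600. The 15% saving is therefore claimed for a covariate set that 10.2 does not use.

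**2. Form of the bias**

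Let b be the log-odds lost per hour of later reperfusion, and d the difference between arms in mean reperfusion time, in hours, caused by allocation. Adjusting for reperfusion time multiplies the estimated common odds ratio (cOR) by about exp(b × d). The factor is above 1 if stenting delays reperfusion, 1 if d = 0, and below 1 if stenting shortens the time.

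**3. Inputs**

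- Margin: cOR 0.8 (4.5). Deferred-group mRS 0–2: 6.9 + 20.2 + 17.9 = 45.0% (4.5).
- 6% per hour (11.2). The protocol does not say whether this is absolute or relative; applying it to 45% mRS 0–2 is an assumption.
  - Absolute, 45% to 39%: b = logit(0.45) − logit(0.39) = 0.247.
  - Relative, 45% to 42.3%: b = logit(0.45) − logit(0.423) = 0.110.
- Standard error of log cOR at 588 patients: √(12 / [588 × (1 − Σp³)]). Here p is the mean of the deferred-group distribution and that distribution shifted by cOR 0.8, which gives Σp³ = 0.026 and a standard error of 0.145.
- d: not in the protocol. Arm-wide mean differences of 10, 20 and 30 minutes are assumed.

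**4. Result when the true total cOR is exactly 0.80**

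False non-inferiority rate = 1 − Φ(1.96 − b × d / 0.145), for one test.

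| Mean delay | Absolute: cOR estimated | Absolute: false rate | Relative: cOR estimated | Relative: false rate |
|---|---|---|---|---|
| 0 min | 0.80 | 2.5% | 0.80 | 2.5% |
| 5 min | 0.82 | 3.5% | 0.81 | 2.9% |
| 10 min | 0.83 | 4.7% | 0.81 | 3.3% |
| 20 min | 0.87 | 8.2% | 0.83 | 4.4% |
| 30 min | 0.90 | 13.4% | 0.85 | 5.7% |
| −10 min | 0.77 | 1.2% | 0.79 | 1.9% |

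**5. Check by simulation**

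Proportional-odds data, 600 patients, true total cOR 0.8, 1,500 runs per setting; b and d again assumed.

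| d, b | Adjusted for a pre-randomisation time | Adjusted for reperfusion time |
|---|---|---|
| +15 min, 0.10 | 0.80, 2.4% | 0.82, 4.1% |
| +20 min, 0.20 | 0.80, 2.7% | 0.85, 6.5% |
| +30 min, 0.25 | 0.80, 2.3% | 0.91, 13.1% |
| none, 0.25 | 0.80, 2.3% | 0.80, 2.4% |
| −15 min, 0.25 | 0.80, 3.1% | 0.75, 0.9% |

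The simulation agrees with the formula. With a pre-randomisation time the estimate stays at 0.80 and the error rate near its nominal 2.5% in every setting.

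**The case against.** The strongest reply is that bias is possible but not shown. It needs allocation to change reperfusion time, or to change which patients have a value. If the stent is placed after thrombus removal it cannot delay reperfusion, and the protocol gives neither the share of patients stented first nor any delay. The direction is also open: section 1 reports that some interventionists regard stenting as necessary for a successful thrombectomy, which suggests it may shorten the time. Section 5.1 allows angioplasty in the control arm to gain access, which takes time too, and only the difference between arms counts. All of this stands. A reader might infer that the estimate is biased, and towards non-inferiority; the document does not support that.

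The upper figures need equal care. If half the stenting arm were stented first, an arm-wide mean delay of 30 minutes would need about 60 extra minutes in each of those patients, before control-arm angioplasty time is subtracted. The rates are for one test; since both analysis sets must succeed, the joint rate cannot exceed them.

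A reader might also infer that the model is undefined for patients who do not reperfuse. That goes too far. A TICI score below 2b is not absence of reperfusion, since grade 2a is partial perfusion, and a coding rule may sit in an analysis plan not shown here. Nor is the adjusted estimate stated to be decisive; the 15% reduction only implies it, and the unadjusted estimate does not have this problem. The presence or absence of sex in the list is an inconsistency and causes no bias.

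None of this supports keeping the covariate. The validity of the test should not depend on the order in which operators work.

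**Conclusion.** The concern holds as a possible bias of unknown size and direction, together with a definite inconsistency. It is certain that the Summary and 10.2 name a time normally fixed after randomisation, that allocation can affect it under 5.1, and that 4.5 takes its sample-size saving from a different, pre-randomisation time.

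The consequence is conditional. Under assumed arm-wide mean delays of 10 to 30 minutes and 6% per hour applied to 45% mRS 0–2, the false non-inferiority rate of a single test is about 3–6% on the relative reading and 5–13% on the absolute reading, against 2.5%. The 13% is a worst case among assumed scenarios. With no difference between arms in reperfusion time there is little or no bias; with a shorter time under stenting, the bias runs against stenting. The change should be made before the analysis because it concerns the covariate set of the primary model and is easy to make.

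**What to change.** - In the Summary and 10.2, replace onset-to-reperfusion time with time from onset (or last seen well) to randomisation, as 4.5 already assumes.
- Use one covariate list in the Summary, 4.5 and 10.2, with sex either in all three or in none.
- State in 10.2 that the adjusted estimate is the one tested against 0.8, in both analysis sets.
- In 10.3, cite 10.2 instead of 10.1, so that the corrected list also applies to the secondary endpoints.
- Report reperfusion time by arm as a descriptive process measure only.

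The cost is protocol wording. The planned 600 patients do not change. Section 8.1.4 names stroke onset among the recorded times but not randomisation time; its list is open and the web-based system would be expected to log it. The sponsor should confirm this, including for randomisations through the telephone back-up. A secondary advantage is that the baseline time has a value for every patient, including those who never reperfuse.

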### **10.3 Secondary study parameter(s)**

Secondary effect parameters will be assessed with linear, logistic or ordinal regression, where appropriate, with the same adjustments as reported in 10.1.

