#### 8.1.2 Secondary study parameters/endpoints (if applicable)

Secondary endpoints are:

- mRS score of 0-1 at 90 days
- mRS score of 0-2 at 90 days
- mRS score of 0-3 at 90 days
- NIHSS score at 24 hours and day 5-7, or at discharge
- adequate recanalization after EVT (TICI 2b or higher)
- final infarct volume on brain CT at 24 hours
- arterial occlusive lesion (AOL) score on CTA at 24 hours
- any stroke within 90 days
- recurrent ipsilateral TIA/ischemic stroke within 90 days
- Carotid artery re-occlusion at 24 hours and 90 days.
- Mortality at 90 days
- Quality of life (EQ5D-5L) questionnaire at 90 days

For the purpose of health economic evaluation, additional questionnaires will be sent to the study participants at 90 days for measuring loss of productivity (IMTA productivity cost questionnaire (iPCQ)) and medical consumption (IMTA medical consumption questionnaire (iMCQ)).

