#### **8.1.4 Other study parameters**

Event characteristics such as prehospital and intra-hospital time intervals will be documented (such as but not limited to: stroke onset, arrival time primary and comprehensive stroke centers, prior IVT, arrival time angiosuite, time of groin puncture, time of recanalization, time of stent placement and end of procedure,). Baseline demographics, medical history, comorbidities and vascular risk factors will be recorded (such as but not limited to: age, sex, prestroke mRS, previous stroke, previous myocardial infarction, hypertension, hyperlipidemia, diabetes mellitus, atrial fibrillation, peripheral vascular disease, smoking status). Medication at baseline and during follow-up will be assessed (such as but not limited to: antiplatelet therapy, anticoagulant therapy, antihypertensive treatment, lipid lowering drugs). Other variables that will be recorded are: NIHSS score, GCS score, vital parameters, laboratory results (such as but not limited to: renal and liver function, glucose, thrombocytes, CRP), and multiple imaging characteristics (such as but not limited to ASPECTS score on non-contrast CT, infarct core volume, penumbra volume, location of intracranial occlusion on CTA and DSA). Various details regarding the endovascular treatment, study treatment and deferred treatment will be recorded (such as but not limited to: periprocedural general/local anesthesia or conscious sedation, stent type, administration of medication during and after EVT).

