**Merci !**

## **18. IMAGING REQUIREMENTS**

### **18.1 Baseline imaging**

#### **WHEN**

1. Before randomization NCCT and CTA study should be performed to assess eligibility for the study.

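### Section 10.3 uses one covariate set for all secondary endpoints, so 24-hour infarct volume is modelled without a baseline tissue measure: a minor, avoidable loss of precision

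*Protocol*

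**What the plan says.** Section 10.3 gives one adjustment rule for every secondary endpoint: "Secondary effect parameters will be assessed with linear, logistic or ordinal regression, where appropriate, with the same adjustments as reported in 10.1". Section 10.1 describes the full analysis, per-protocol and safety sets and names no covariate. The only covariate list in chapter 10 is in 10.2, where the primary model is "adjusted for age, baseline NIHSS score, pre-stroke mRS score, collateral score on baseline CTA and onset to reperfusion time".

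The secondary endpoints in 8.1.2 include "final infarct volume on brain CT at 24 hours", "arterial occlusive lesion (AOL) score on CTA at 24 hours", TICI 2b or higher, and carotid re-occlusion at 24 hours and 90 days.

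Among the imaging variables recorded, 8.1.4 lists "ASPECTS score on non-contrast CT, infarct core volume, penumbra volume, location of intracranial occlusion on CTA and DSA". Section 15.5 describes ASPECTS as a score of early ischemic change on the pretreatment non-contrast CT, and 18.1 makes that scan mandatory: "Before randomization NCCT and CTA study should be performed to assess eligibility for the study". In 10.4, ASPECTS, intracranial occlusion location and degree of carotid disease appear as subgroup variables.

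**The concern.** The list in 10.2 was drawn up for the 90-day mRS. Applied to infarct volume at 24 hours, it contains no measure of the ischemic change already visible before treatment, which is an obvious candidate predictor of the final volume. The NIHSS endpoint does get its own baseline value under the same rule, because baseline NIHSS is in the list. Infarct volume gets no counterpart.

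What is at stake is the width of the confidence interval for one secondary endpoint. Because the protocol states the set for all secondary endpoints, an analysis plan that added ASPECTS would depart from its text. This is therefore not simply a detail left open for the analysis plan. The wrong cross-reference is a second reason to rewrite the sentence: read literally, 10.3 carries over no covariates at all.

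**Working it through.** **1. Which list is meant, and does it matter?** The protocol gives three covariate lists:

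- Section 10.2: "adjusted for age, baseline NIHSS score, pre-stroke mRS score, collateral score on baseline CTA and onset to reperfusion time".
- Summary: "age, sex, baseline NIHSS, prestroke mRS score, collateral score on baseline CTA and onset to reperfusion time", which adds sex.
- Section 4.5: "age, pre-stroke mRS score, stroke severity, collateral score and time from symptom onset to randomization", which uses time to randomisation instead of time to reperfusion.

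None contains ASPECTS, core volume, occlusion site or cervical lesion type. Whichever list is intended, infarct volume is modelled without a baseline tissue measure. The collateral score is the only baseline imaging variable in any of them.

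**2. The plan's own figure.** The protocol gives no precision or power figure for a secondary endpoint, so there is none to reproduce. Its only figure for covariate adjustment is in 4.5 and concerns the primary endpoint: a reduction of at least 15%, 610 × 0.85 = 518.5, stated as 520. It shows that the plan accepts the principle. It says nothing about infarct volume.

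**3. Infarct volume (linear model).** Let R² be the share of the residual variance, after the 10.2 covariates and treatment, that ASPECTS explains. Then

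- SE with ASPECTS / SE without = √(1 − R²)
- number of patients analysed without ASPECTS that would match 600 analysed with it = 600 / (1 − R²)

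The total of 600 is from 4.5. R² is an assumption, because the documents give no correlation or standard deviation for infarct volume.

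| Assumed R² | SE ratio | SE falls by | 600 patients worth |
|---|---|---|---|
| 0% | 1.000 | 0% | 600 |
| 5% | 0.975 | 2.5% | 632 |
| 10% | 0.949 | 5.1% | 667 |
| 20% | 0.894 | 10.6% | 750 |
| 25% | 0.866 | 13.4% | 800 |

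A simulation of the linear model with 600 patients agreed with the formula. At partial correlations of 0.2, 0.4 and 0.6 the simulated SE ratios were 0.980, 0.917 and 0.803, against 0.980, 0.917 and 0.800 from √(1 − r²).

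**4. Binary and ordinal imaging endpoints.** The formula in step 3 does not apply to logistic or ordinal models. A logistic model was simulated with 600 patients, an assumed treatment log odds ratio of 0.4 and an added covariate of assumed strength:

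| Covariate log odds per SD | SE of log OR, without → with | z, without → with |
|---|---|---|
| 0.5 | 0.193 → 0.198 | 2.06 → 2.09 |
| 1.0 | 0.186 → 0.203 | 1.77 → 1.92 |

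The SE rises when the covariate is added. The estimate moves further from zero, so z, and with it power, rises modestly.

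**5. Is the extra variable available?** For ASPECTS, yes: the scan it is read from is required before randomisation (18.1), and chapter 10 provides for imputing missing baseline data. For perfusion core volume this is uncertain. Section 8.3 says all patients receive perfusion CT at baseline, 18.1 requires only non-contrast CT and CTA, and 4.3 ties perfusion selection to the 6-24 hour window.

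**The case against.** The strongest reply is that a common prespecified set is valid. Randomisation protects the comparison, chance imbalance is already reflected in the interval, and a different covariate choice is a matter of efficiency. That stands, and it is why the point is minor. A reader might infer that the infarct-volume comparison is biased without ASPECTS; the randomised design does not support that.

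Three other stronger readings also fail.

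- **All imaging endpoints lose precision.** Only infarct volume is a linear-model endpoint. For TICI, AOL and carotid re-occlusion, step 4 shows a modest gain in power with a larger, not smaller, SE of the log odds ratio.
- **Each imaging endpoint lacks its own baseline value.** Occlusion site is not a baseline TICI or AOL score, and no such score is listed. ASPECTS is a baseline correlate of infarct volume, not a baseline infarct volume.
- **Power rises from 80% by a stated amount.** The 80% in 4.5 belongs to mRS non-inferiority. No secondary endpoint is powered, so the SE reduction cannot be turned into a power figure for infarct volume.

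It is also fair to say that the assumed 5-25% has no source in the documents, and that NIHSS and collateral score may already account for part of it.

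Finally, onset-to-reperfusion time, in the same list, is measured after randomisation and can be affected by stenting before thrombectomy. That is a separate and weightier matter, and adding ASPECTS does not resolve it.

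**Conclusion.** The point holds as a minor efficiency finding. Section 10.3 fixes one covariate set through a wrong cross-reference, and as a result 24-hour infarct volume is modelled without a baseline measure of ischemic tissue that the trial already records.

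The direction is certain if ASPECTS predicts infarct volume beyond the listed covariates. The size is not: the SE falls by about 3-13% if the further share of residual variance explained is 5-25%, and by nothing if it is zero. This rests on a linear model for infarct volume, transformed if needed, and on reading 10.3 as pointing to 10.2. The validity of the comparison and the primary analysis are unaffected.

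**What to change.** Rewrite the sentence in 10.3 to:

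1. refer to 10.2 instead of 10.1;
2. keep the common set as the default and add baseline ASPECTS, as a score, to the infarct-volume model.

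Optionally, add intracranial occlusion site for TICI and AOL, and baseline cervical stenosis versus occlusion for carotid re-occlusion, on the understanding that the expected benefit is a modest rise in power.

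Do not make perfusion core volume a required covariate unless 8.3 and 18.1 are reconciled and it is available in all patients. A covariate used only where available is not a defined model.

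The cost is one sentence in the protocol and its counterpart in the analysis plan. No new scan, visit or data item is needed. The change should be made before unblinding, because covariates added later would look data-driven.
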